- Smoking
- Diabetes
- Urinary tract infection history
- Current medication use

Physical Examination

- Height and weight

Surgery should be scheduled and performed within 4 months. If more than 4 months transpires before surgery, baseline instruments will need to be re-administered.

H. Randomization

After eligibility is determined and consent is obtained from the participant, the participant will be randomized to one of the two treatment arms using a web-based randomization system. To minimize any risk of selection bias resulting from clinician knowledge of current or future treatment assignments, each participant will be randomized by the surgeon when the participant is in the operating room. The participant will be randomized to one of two apical procedures: either a vaginal hysterectomy with USLS or mesh strap vaginal hysteropexy (Uphold® procedure), with the randomized procedure provided to the surgeon for each participant individually in the operating room immediately prior to the surgery. Other native tissue vaginal wall prolapse repairs (e.g., anterior colporrhaphy, posterior colporrhaphy, perineorrhaphy) will be allowed as needed.

Randomization (1:1 to the two treatment arms) will be performed using permuted blocks, with a block size that is known only to the DCC and will be stratified by site. For each participant, the web-based system will determine the treatment allocation from a static randomization table developed by the study randomization statistician prior to the start of the study. Only the study

statistician and randomization system programmer will have access to the randomization table to minimize the risk of selection bias.

I. Appointment Scheduling

Routine clinical practice postoperative visits will take place during the 12 week postoperative period with the inclusion of one study visit at 6 weeks to assess for early outcomes. The 6 week in person visit and the in person visits every 6 months for the duration of the study will capture the following outcomes:

- 1) Urinary function including duration of post-op catheterization and de novo voiding dysfunction rates. A PVR will be assessed by catheterization or bladder scan at the 6 week visit and this is defined as an elevated postoperative post void residual > 150 ml that was not present preoperatively.
- 2) De novo incontinence rates and severity assessed by the UDI-6, ISI, and AE survey
- 3) Functional activity by administration of the Functional Activity Assessment Scale⁴²

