- 4) Mesh-related complications: mesh exposure in the vagina or mesh erosion into another organ and the classification of the intervention:
 - a) None or non-surgical medical intervention only
 - b) Minor or intra-office surgical intervention
 - c) Outpatient surgery
 - d) Inpatient surgery
- 5) Rates, location, and severity of pelvic pain using the modified Surgical Pain Scale that has demonstrated validity and responsiveness in OPTIMAL⁴³, pain medication use, AE survey, and Pain Mapping Instrument
- 6) Pelvic infection:
 - a) Perioperative infections, defined as requiring antibiotics
 - b) Urinary tract infections, defined as culture proven or antibiotics given
 - c) Vaginal infections with flora uncommon to the vaginal canal
- 7) Neuromuscular problems (including groin and leg pain) with the use of the Pain Mapping Instrument
- 8) Vaginal scarring, vaginal shortening, de novo dyspareunia, and worsening dyspareunia with AE survey

Subsequent study visits will then occur at 6 month intervals for up to 60 months for collection of all study measures.

J. Interventions – Surgical Interventions

J.1 Surgeon Experience and Certification

Experience

To reduce bias related to surgical experience, surgeons should be experienced with all procedures being performed in this study. For the native tissue arm in this study, surgeons need to be experienced with vaginal hysterectomy and uterosacral ligament suspension and for the uterovaginal Uphold® procedures, surgeons need to be experienced with the Uphold® procedure.

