 - b) Urinary – urinary function including duration of post-op catheterization, mean UDI-6 scores⁴⁹, Hunskar Incontinence Severity Index, de novo voiding dysfunction rates, de novo incontinence rates
 - (i) Sexual – mean PISQ-IR⁵⁰ and specific rates of de novo dyspareunia
 - (ii) Bowel – bowel function using CRADI-8 scores⁴⁹
 - (iii) QOL – general SF-12 scores and sub-scales⁵¹, and Pelvic QOL mean PFIQ score⁴⁹; Functional Activity Assessment Scale⁴²

Secondary Aim 2 – Safety: These measures will require a statistical analysis plan and will be reported in the primary outcome manuscript.

- 1) Intraoperative safety – group comparisons of mean Operative time, estimated blood loss, blood transfusion, intra- and post-operative complications categorized using a modification of the Dindo Classification.⁵²
- 2) Adverse events – mesh related complications: mesh exposure in the vagina or mesh erosion into another organ and the classification of the intervention:
 - a) none or non-surgical medical intervention only

Confidential Please Do Not Copy

- b) minor or intra-office surgical intervention
- c) outpatient surgery
- d) inpatient surgery

Other complications possible in both arms:

- 1) Rates of pain captured from the modified Surgical Pain Scale⁴³, pain medication use, and location of pain with Pain Mapping Instrument
- 2) Pelvic infection:
 - a) perioperative infections
 - b) urinary tract infections
 - c) vaginal infections with flora uncommon to the vaginal canal
- 3) Vaginal shortening, de novo vaginal bleeding, atypical vaginal discharge, fistula formation, neuromuscular problems (including groin and leg pain)
- 4) Need for subsequent procedures – any surgical or non-surgical treatment for pelvic floor disorders (including urinary incontinence, voiding dysfunction, defecatory dysfunction or fecal incontinence, recurrent prolapse, and dyspareunia/pelvic pain). Any subsequent uterine or cervical office or Operating Room procedure in hysteropexy group (e.g., cervical biopsy, LEEP, hysteroscopy, D and C, hysterectomy).
- 5) Subsequent uterine or cervical pathology
- 6) Rates of vaginal scarring defined as de novo vaginal scar requiring medical or surgical intervention or adversely affecting quality of life
- 7) Rates of vaginal shortening, de novo dyspareunia, and worsening dyspareunia with AE survey instrument

Complication Monitoring

Groups will be compared for rates of “important complications”. The definition of “important complication” is:

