Perception of commercial bias: It is not unprecedented for a NIH-funded network to study a specific product (e.g., Botox, InterStim in the PFDN; Gynecare TVT, TVT-O and AMS Monarc in the UITN TOMUS study). If a non-commercial, home-made mesh bridge device was studied and proven inferior, proponents could argue it was the fault of a non-standardized device. For this reason, we favor a hysteropexy kit that lends itself to standardization. It is likely that industry funding will be available for this study, but industry will not participate in data collection, data analysis, or manuscript preparation.

P.2 Informed Consent

Patients who are candidates for study participation will be approached for enrollment. Written informed consent will be obtained in accordance with Institutional Review Board guidelines.

A common template for informed consent will be used by all centers, with modifications allowed to meet the necessary requirements of their respective institutional human subjects committees.

Uterovaginal Prolapse: Eligible women will be informed that traditional treatment for uterine prolapse includes hysterectomy with native tissue suture support; but more recently an option is uterine sparing with a mesh graft suspension and we do not know which procedure is more successful or more durable. Advantages of hysterectomy include eliminating the possibility of future uterine or cervical pathology while the disadvantages are the removal of a normal organ, possible earlier menopause, and the risks of intra-peritoneal injury, intra-abdominal bleeding and vaginal shortening. The advantage of the hysteropexy procedure includes preservation of a normal organ, normal timing of menopause, and decreased risk of intra-peritoneal complications. The disadvantages include possible future uterine or cervical pathology requiring additional surgery. All patients will be made aware of the risks of transvaginal mesh included in the FDA warning (e.g. mesh erosion, pelvic pain, and dyspareunia) via the study informed consent statement.

P.3 Data and Safety Monitoring Board

The NICHD has established a Data Safety Monitoring Board (DSMB) to oversee this study. Members of the DSMB are independent of the study investigators and include representatives with urology, urogynecology, and biostatistics expertise and a lay member. The DSMB will have regularly scheduled meetings, either in person or by teleconference. The Chair may request to meet more frequently.

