9.2 Efficacy Variables

Variable	Туре	Definition
Primary Outcome		
Treatment failure/success obtained at 6-month intervals for a period of 3 to 5 years after surgery	Binary	Treatment failure will be defined as the occurrence of any ONE of the following criteria: (1) report of bothersome vaginal bulge symptoms (see definition below); (2) re-treatment for prolapse (surgery or pessary); or (3) any prolapse measure (Ba, C, Bp) is beyond the hymen (i.e. >0 cm). Bothersome vaginal bulge symptoms are defined as positive response to Question 3 of the PFDI-20: Do you usually have a bulge or something falling out that you can see or feel in your vaginal area? AND any degree of bother.
Secondary Efficacy Out	comes	
Anatomical measures of key pelvic floor metrics (Ba, Bp, and C) obtained at 6-month intervals post-operatively	Continuous	Data measurements obtained directly from the POPQ exam.
Anatomical measure of cervical or cuff location relative to total vaginal length	Binary	Obtained by comparing the cervical or cuff location (Point C) to the total vaginal length (TVL) from the POPQ exam obtained at 6-month post-operative intervals. A participant will be defined as positive at any time point if $C > -1/2$ TVL.
Prolapse symptoms at 6- month post-operative levels as defined by	Binary	The PGI-I is a single question form collected every 6 months that asks for a response to the question: "Check the number that best describes how your post-operative condition is now, compared with how it was before you had the surgery." The response is a 7-level Likert scale from 1 Very much better to 7 Very much worse. If the participant response is either 1 (very much better), 2 (much better), and 3 (better) then the indicator will be coded as Yes. If the participant response is 4 or greater, the indicator will be coded as No. If the PGI-I is missing for a visit then the indicator will be coded as missing for that visit.

Variable	Туре	Definition
Prolapse symptoms at 6- month post-operative levels as defined by POPDI-6 scores from the PFDI-SF	Continuous	The PFDI-SF Pelvic Organ Prolapse Distress Inventory (POPDI) scale will be computed at 6 month intervals using standard scoring algorithms described by Barber (2006) to create a measure scaled 0 to 100 at each time point based in data collected on the PFDI. If data at any month are missing, the outcome variable will be coded as missing for that month. All longitudinal analyses or time-specific analyses will use all available data.

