Duration of post-operative catheterization	Continuous	Time to removal of the catheter post-operatively obtained directly from CRF data.
Urinary functional distress as measured PFDI-SF Urinary Distress Inventory scale at 6- month post-operative intervals	Continuous	The PFDI-SF UDI scale will be computed at 6 month post-operative intervals using standard scoring algorithms described by Barber (2006) to create a measure scaled 0 to 100 at each time point. If data at any month are missing, the outcome variable will be coded as missing for that month. All longitudinal analyses or time-specific analyses will use all available data.
Incontinence severity at 6- month post-operative intervals as measures by the Hunskaar Incontinence Severity Index	Ordinal	The ISI scale will be computed at 6-month post operative intervals using the standardized scoring algorithm to generate an ordinal scale (no incontinence or incontinence levels of slight, moderate, severe, or very severe) as described by Sandvik (2000).
Risk of de novo voiding dysfunction defined at 6- month post-operative intervals (evaluated in aggregate fashion)	Binary	Defined as any incidence of a specific voiding dysfunction based on patient-supplied AE information. Rather than reporting data at six-month intervals, results will be aggregated across the follow-up period based on decision at masked review.

Variable	Туре	Definition
Risk of de novo incontinence defined at 6-month post- operative intervals (evaluated in aggregate fashion)	Binary	Defined as any incident case of new or worsening stress urinary incontinence or new or worsening urgency urinary incontinence as reported on either the Patient-reported AE forms or on the complication form obtained at six-month intervals. Based on masked data review, results will be aggregated across the reporting period rather than evaluated at six-month intervals

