Operative time	Continuous	Obtained directly from peri-operative form			
Blood loss	Continuous	Obtained directly from peri-operative form			
Blood transfusion	Binary	Obtained directly from peri-operative form			
Complications	Ordinal	All complications will be collected and scored on a five- point ordinal scale using the Dindo classification scheme (Dindo, 2004). Each participant will then be classified according to the most severe complication			
Routinely Collected	Adverse Events				
Mesh-related Complications	Ordinal	Mesh related complications: mesh exposure in the vagina or mesh erosion into another organ; note that level of complication will be characterized into based on the following response classification schema: (a) None or non-surgical medical intervention only; (b) Minor or intra-office surgical intervention; (c) Outpatient surgery; (d) Inpatient surgery			
Pelvic infection	Binary	Any incident of pelvic infection will be captured as a Ye response (AE or SAE) to Question 13 in the complication section of the Hospitalization form or Question 14 of the follow-up evaluation form. It will also be captured base on open-ended AE responses with comments indicative pelvic infection.			
Perioperative infection	Binary	A perioperative infection will be captured as a Yes response (AE or SAE) to one or more of Questions 13, 14, 22, 23, 24, or 25 of the Hospitalization form or Questions 15, 16, 17, 18, 19, or 10 of the Post-operative visit form.			

UTI	Binary	A UTI will be captured as a Yes response (AE or SAE) to Question 23 of the Hospitalization form, Question 18 of the Post-operative visit form, or Question 20 or the 6- to 60- Month Study follow-up form or by an event classified as a Urinary Tract Infection based on Preferred terms in the AE form.		
Vaginal infections	Binary	A Vaginal Infection will be captured as a Yes response (AE or SAE) to Question 22 of the Hospitalization form, Question 17 of the Post-operative visit form, or Question 19 or the 6- to 60- Month Study follow-up form or by an event classified as a vaginal infection based on either the preferred term or comments for an event on the AE form.		
Vaginal shortening	Binary	Vaginal shortening will be determined by an event classified as a vaginal shortening based on either the preferred term or comments for an event on the AE form.		

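### The SAP scores de novo voiding dysfunction without the protocol's 6-week PVR criterion and gives no reason; separately, measured vaginal length is not used alongside adverse-event reports of shortening.

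*SAP*

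**What the plan says.** **Voiding dysfunction.** Protocol section I schedules a PVR by catheter or bladder scan at the 6-week visit, and of de novo voiding dysfunction says that "this is defined as an elevated postoperative post void residual > 150 ml that was not present preoperatively". The footnote to Protocol Table 4 lists PVR in the 6-week recovery assessment, and Protocol M.2 lists de novo voiding dysfunction rates among the secondary efficacy outcomes. SAP 9.2 defines the outcome as "Defined as any incidence of a specific voiding dysfunction based on patient-supplied AE information" and adds that masked review led to pooling over follow-up. It has no PVR criterion. Apart from the abbreviation list, PVR appears in the SAP only in the baseline-characteristics shell. SAP 14 is left for later completion.

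**Vaginal shortening.** SAP 10.2: "Vaginal shortening will be determined by an event classified as a vaginal shortening based on either the preferred term or comments" on the AE form. The protocol also uses the AE survey, in section I ("Vaginal scarring, vaginal shortening, de novo dyspareunia, and worsening dyspareunia with AE survey") and in M.2 ("Rates of vaginal shortening, de novo dyspareunia, and worsening dyspareunia with AE survey instrument"). Protocol P.2 counts among the disadvantages of hysterectomy "the risks of intra-peritoneal injury, intra-abdominal bleeding and vaginal shortening". TVL is measured: for the apical outcome, SAP 9.2 compares point C "to the total vaginal length (TVL) from the POPQ exam obtained at 6-month post-operative intervals". No TVL mean, change score or threshold for shortening is planned.

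**Status.** SAP 7.7 makes secondary outcomes exploratory and safety p-values descriptive.

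**The concern.** For voiding, the protocol names an objective measurement, a cut-off, a visit and a preoperative comparison. The SAP has a count of patient-supplied events with none of these. The two can classify the same woman differently: a residual of 200 ml at 6 weeks without complaint is a case under the protocol and may not be one under the SAP, while a voiding complaint at month 30 is the reverse. A reader of the results would have no notice of the change.

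For shortening, a harm the consent discussion attaches to one arm is compared only through what is entered on the AE form. A line showing few or no events in either arm could be read as evidence that length was preserved, although the study measures length and could report it. These outcomes feed the primary manuscript and the FDA-required report described in SAP 2.

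**Working it through.** The documents give no rate, effect size or power for either outcome, so there is no planned figure to reproduce. The main check is a comparison of definitions.

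| | Protocol | SAP |
|---|---|---|
| Voiding: source | measured PVR | patient-supplied AE information |
| Voiding: criterion | above 150 ml, absent before surgery | any incident event |
| Voiding: timing | 6 weeks | pooled over follow-up |
| Shortening: source | AE survey | AE-form preferred term or comments |
| Shortening: use of TVL | none | none |

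On voiding, the documents differ in source, criterion and timing. The pooling is attributed to masked review; the omission of PVR is not explained. On shortening they agree in kind, with the SAP somewhat narrower.

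**How cases could be missed.** SAP 10.2 has the study coordinator complete the AE logs. Under Protocol J.3 the coordinator stays masked and a different person does the POPQ. The SAP gives no rule that turns a measured loss of TVL into an AE entry. Most neighbouring rows of the safety table (infections, bleeding, discharge, fistula, neuromuscular problems) cite a numbered form question; the shortening row cites none.

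**Illustration 1: incomplete capture.** Arm sizes of 87 and 88 come from the SAP display shells. True rates and the captured fraction Se are assumptions, with no false positives.
- Observed rates are Se × p1 and Se × p2, so the risk difference shrinks by the factor Se and the relative risk is unchanged.
- Power = Φ[(d − 1.96 × se0)/se1], where d is the observed difference and se0 and se1 are its pooled and unpooled standard errors.
- At 20% against 10% with Se = 1: d = 0.10, se0 = 0.0539, se1 = 0.0535. Then (0.10 − 0.1057)/0.0535 = −0.107, giving power 0.46.

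| Assumed true rates | Se = 1 | 0.75 | 0.50 | 0.25 |
|---|---|---|---|---|
| 20% v 10% | 0.46 | 0.35 | 0.24 | 0.14 |
| 15% v 5% | 0.60 | 0.47 | 0.33 | 0.18 |

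Unequal capture is worse. With 20% true in both arms and Se of 0.50 against 0.25, the observed rates are 10% and 5%, a difference that does not exist.

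**Illustration 2: what TVL would add.** The 95% half-width for a difference in mean TVL change is 1.96 × SD × √(1/88 + 1/87), which is 0.30 cm for SD 1.0 and 0.44 cm for SD 1.5. The SDs are assumed, and every woman is taken to have data. By contrast, 0 AE reports among 88 women gives an exact 95% upper limit of 1 − 0.025^(1/88) = 4.1% for reported events, and says nothing about length.

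**Illustration 3: effect on the apical outcome.** With C = −4 cm, a woman with TVL 10 cm is positive for C > −TVL/2 (−4 > −5), and one with TVL 6 cm is negative (−4 is not > −3). Without TVL beside it, better support and a shorter vagina cannot be told apart.

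**The case against.** **The SAP follows the protocol on shortening.** This stands. A reader might infer that the SAP replaced a measured shortening outcome, but the protocol names the AE survey twice and never lists TVL as an outcome. A TVL analysis is an addition, not a correction.

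**Under-reporting is not shown.** This also stands. A reader might infer that both comparisons rest on under-counted events, or that no prompted question exists for shortening. The case report forms are not in the documents, and SAP 10.2 says targeted complications are asked about at visits and automatically populate the AE form. The voiding information may also come partly from prompted questions.

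**PVR cannot replace the AE count.** It is scheduled after surgery only at 6 weeks, so using it as the sole definition would discard every later event. It can define the early outcome only. Pooled reports also add later cases, so whether the AE count exceeds or falls short of the 6-week PVR count is unknown.

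**Other voiding data remain.** The SAP has catheterisation duration, spontaneous voiding at discharge and urinary retention events. They are useful, but none is a 6-week residual.

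**TVL may not compare cleanly.** Protocol B.2 warns that point C is a cuff in one arm and a cervix in the other. The documents do not say whether this affects TVL, and they set no shortening threshold. TVL therefore belongs beside the AE count, not in place of it.

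**Conclusion.** The voiding point holds: a protocol-defined, measured 6-week outcome is absent from the SAP's analysis, with no reason stated and no entry in the section for changes. That rests on the text alone and does not depend on any under-reporting. The shortening point is smaller: the AE-based source is the protocol's own, but a measured quantity that bears directly on the harm goes unsummarised.

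The size cannot be computed from the documents. The illustrations rest on assumed rates, captured fractions and SDs; they show how incomplete capture could weaken or distort a comparison, not that it does so here. Three stronger readings lack support: that events are in fact under-reported, that the SAP contradicts the protocol on shortening, and that TVL should be the main shortening measure. The consequence is confined to descriptive secondary and safety comparisons; the primary outcome is unaffected.

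**What to change.** 1. In SAP 9.2 and 9.4.3, add 6-week de novo voiding dysfunction by arm: PVR above 150 ml among women whose preoperative PVR was not above 150 ml. Report how many women have both measurements. The baseline shell implies a preoperative PVR, but the protocol schedule has no baseline row for it.
2. Keep the AE-based voiding count over later follow-up as a separate, separately named outcome.
3. In SAP 9.4.2, add TVL change from baseline by arm to the continuous anatomic outcomes, and list baseline TVL in the baseline table. Show it beside the AE-based shortening count, with the cuff-versus-cervix caveat. If a shortening threshold is wanted, fix it before unmasking.
4. In SAP 14, record the change in the voiding definition and the reason for it.

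The cost is SAP wording and two descriptive analyses on measurements already scheduled. No new visit or procedure is needed.
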